Progression-free survival (PFS) is defined as the time from the first dose to the first documentation of objective tumor progression, start of alternate therapy or death due to any cause. Patients who do not have disease progression or have not died will be censored at the last known time that the patient was progression free. If a patient begins a new anticancer treatment (either systemic or local) prior to documented progression or death, or if a patient is removed from the study due to undocumented clinical disease progression, then the patient will be censored at the last assessment where the patient was documented as progression free prior to the intervention. Patients with 2 or more consecutive missing response assessments prior to a visit with documented progression (or death) will be censored at the last date of tumor assessment when the patient was documented to be progression free. The detailed censoring rules for PFS is in section 6.2.2.

Progression-free survival will be calculated as follows (in weeks):

(date of disease progression/death – first dose date +1)/7

The survival distribution of PFS will be estimated using Kaplan-Meier methodology. The median PFS will be provided along with the two-sided 95% CIs based on the Efficacy Evaluable population. In addition, Kaplan-Meier curves will be provided. The 6-month PFS rate will be estimated using the Kaplan-Meier estimate.

• Time to Progression:

Time to progression (TTP) is defined as the time from the first dose to the confirmed tumor progression. All events of disease progression will be included regardless of whether the patient discontinued the study drug. If the patient has not experienced disease progression, the patient's data will be censored at the date of last disease assessment. Data for patients without any disease assessments performed after the first dose will be censored at the date of first study drug.

The TTP will be calculated as follows (in weeks):

(date of disease progression – date of first dose + 1)/7

TTP will be analyzed by Kaplan-Meier methodology. Median TTP will be calculated and 95% confidence interval for median TTP will be presented.

• Overall Survival:

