6.2.2. Censoring Rules for Progression Free Survival (PFS)

The Progression Free Survival censoring dates for a patient is listed in Table 5. The start date is the first dose date of the study drug.

Table 5:	Censoring Rules for Progression Free Survival
----------	---

Situation	Date of Progression or Censoring	Outcome
No baseline or unreadable baseline assessment, but readable post-baseline assessments	Date of the 1 st dose of the study drug	Censored
Progression documented between scheduled visits	 Earliest of Date of radiological assessment showing new lesion (if progression is based on new lesion); or Date of last radiological assessment of measured lesions (if progression is based on increase in sum of measured lesions) 	Progressed
Death before first PD assessment	Date of death	Progressed
Death between adequate assessment visits	Date of death	Progressed
Treatment discontinuation for undocumented progression	Date of last tumor assessment with no documented progression	Censored
Treatment discontinuation for toxicity of other reason	Date of last tumor assessment with no documented progression	Censored
Patients still on treatment without PD as of data cut-off	Date of last tumor a ssessment	Censored
Treatment discontinuation for other than PD or death with post-baseline tumor assessments	Date of last tumor assessment	Censored
New anticancer treatment started before PD or death	Date of last tumor assessment before start of new treatment	Censored
Death or PD after two or more missed tumor assessments	Date of the last tumor assessment before missed assessments	Censored
Only NE assessments after CR, PR, SD	Date of last tumor assessment before NE assessments	Censored

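### SAP 3.11.3 lists start of alternate therapy as a PFS event, while its own censoring sentence, its formula and Table 5 censor it; two discontinuation rows in Tables 4 and 5 also need a stated limit

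*SAP*

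**What the plan says.** **PFS definition.** SAP 3.11.3 counts time from first dose to "first documentation of objective tumor progression, start of alternate therapy or death due to any cause".

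**PFS censoring in the same paragraph.** Two sentences on, the rule opens with "If a patient begins a new anticancer treatment (either systemic or local) prior to documented progression or death" and sends that patient to censoring at the last progression-free assessment before the intervention. The PFS formula has progression or death as its only end dates. SAP 6.2.2, Table 5, has a row "New anticancer treatment started before PD or death" with outcome Censored, dated at the last tumor assessment before the new treatment.

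**Stopping treatment.** Table 5 (PFS) and Table 4 (DOR) share two further rows, both with outcome Censored:
- "Treatment discontinuation for toxicity of other reason", dated at "Date of last tumor assessment with no documented progression";
- "Treatment discontinuation for other than PD or death with post-baseline tumor assessments", dated simply at the last tumor assessment.

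The same tables count "Death before first PD assessment" as an event on the date of death. The DOR text in 3.11.3 refers to a section 6.2.3 for its detailed rules. The SAP has no such section, and the number 6.2.1 is used twice (OS and DOR).

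**The concern.** A PFS rule has to say whether starting another therapy ends follow-up as an event or as a censoring. This SAP says both. Two programmers working from different lines of the same section would code the same patient differently.

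The two discontinuation rows raise a related but weaker question. Each describes the reason for stopping and says nothing about what is found afterwards. Read literally, a patient who stops for toxicity and later progresses or dies is censored, although the PFS and DOR definitions in 3.11.3 and the death rows count that event. Protocol 8.3.10.6 likewise runs duration of response to the first objectively documented recurrence or progression, with no stop at discontinuation. Such events can be observed: Protocol Table 4, footnote b, asks for best-effort imaging every 8 weeks after study therapy stops.

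At stake are the Kaplan-Meier estimates of PFS and DOR. The primary objective improvement rate does not use these rules.

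**Working it through.** The documents state no PFS or DOR figure that depends on these rules, so there is nothing to reproduce. The check is a comparison of the text, with worked dates.

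**1. New therapy before progression or death**

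| Statement | Treatment of new therapy |
|---|---|
| 3.11.3, PFS definition | Event |
| 3.11.3, third sentence of the PFS paragraph | Censored |
| 3.11.3, PFS formula | No term for it |
| 6.2.2, Table 5 | Censored |

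Protocol 13.4.2 plans PFS curves without defining the event or the censoring, so it does not settle the matter.

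Worked patient, with Day 1 as first dose: (date − first dose date + 1)/7 is then the study day divided by 7. Stable-disease scan on day 43, new therapy on day 60, no progression or death before it.
- By the definition: event at 60/7 = 8.6 weeks.
- By the censoring sentence and Table 5: censored at 43/7 = 6.1 weeks.

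*Illustration of size; every input is assumed.* Let PFS be exponential with rate λ = ln 2/median. Let a share q of patients start new therapy first, independently of progression, at rate μ = λq/(1 − q). Six-month PFS is exp(−6λ) if new therapy is censored and exp(−6(λ + μ)) if it is an event.

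| Assumed median | Censored | Event, q = 10% | Event, q = 20% | Event, q = 30% |
|---|---|---|---|---|
| 3 months | 25.0% | 21.4% | 17.7% | 13.8% |
| 6 months | 50.0% | 46.3% | 42.0% | 37.1% |

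The gap is about 4 points (25.0 − 21.4 = 3.6) to 13 points (50.0 − 37.1 = 12.9). This calculation censors at the start of therapy, not at the preceding scan, and so ignores the scan schedule.

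**2. The two discontinuation rows**

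A toxicity stop with a post-baseline scan meets both rows. Two patients, each with a stable-disease scan on day 43 and a toxicity stop on day 50:

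| Later course | 3.11.3 definition | Toxicity row | Other-than-PD-or-death row |
|---|---|---|---|
| Progression on a scan on day 106 | Event, 106/7 = 15.1 weeks | Censored, 43/7 = 6.1 | Censored, 106/7 = 15.1, if the progression scan is taken as the last assessment |
| Death on day 75, no earlier progression | Event, 75/7 = 10.7 weeks | Censored, 6.1 | Censored, 6.1 |

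Day 106 is 56 days after the stop, which is the first 8-weekly scan under footnote b. Protocol Table 5 leaves imaging after a non-progression stop to local practice, so that date is an assumption.

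Neighbouring rows do carry limits, for example "Patients still on treatment without PD as of data cut-off" and "New anticancer treatment started before PD or death". If the two rows were limited in the same way to patients with no later event, both patients above would be events and the two censoring dates would normally coincide. That limit is not written, and no order of precedence among rows is given.

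I give no percentage for this part. It would depend on how many patients stop early, how they fare afterwards, how often later scans are captured, and the scan schedule. The protocol describes that schedule in different ways: Table 4 as printed marks weeks 6, 10 and 16; its footnote s says 6 weeks and then every second cycle; Tables 5 and 7 say week 9 and then every third cycle.

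**The case against.** **One phrase stands against three consistent statements.** The PFS paragraph refers the reader to 6.2.2 for detail, and Table 5, the censoring sentence and the formula agree. This makes the intent fairly clear and supports deletion as the repair. It does not make the definition correct.

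**Censoring at discontinuation may be deliberate.** The TTP paragraph of 3.11.3 counts every progression whether or not study drug had stopped; the PFS and DOR paragraphs have no such sentence. SAP 6.2 also says that its rules follow a cited guidance, which cannot be checked from the documents. This objection stands. A reader might infer that the two rows certainly discard valid events, but the documents do not support that: the narrower reading is plausible and the intent is open.

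**The coding may be settled elsewhere.** Dataset and programming specifications are separate documents (SAP sections 6 and 8). They may fix the precedence, but the SAP would still contradict itself.

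**Stops for undocumented progression.** A reader might see a third contradiction here, because the note to Protocol Table 8 asks sites to document objective progression even after such a stop. For PFS there is none: 3.11.3 and Table 5 both censor these patients, and the protocol note concerns data collection. What happens if progression is then documented is an unaddressed edge case.

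**Conclusion.** The first part holds without qualification: the PFS definition is contradicted by its own paragraph, its formula and Table 5. For a single patient the difference is event at 8.6 weeks against censored at 6.1 weeks. The 4 to 13 point gap in six-month PFS illustrates what could follow if 10% to 30% of patients start new therapy first, with a median of 3 to 6 months and independence from progression. None of those inputs is in the documents.

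The second part holds as a need for reconciliation. The two rows overlap, carry different dates and lack a stated limit, and read literally they conflict with 3.11.3 and the death rows. A reader might infer a bias of known size or direction in PFS; the documents do not support one, since both depend on assumed rates and on the scan schedule. The widest date conflict also requires a scan that shows progression to be used as a censoring date, which is an unlikely way to program the row.

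The consequence is confined to the secondary, descriptive PFS and DOR estimates. The correction is worth making before analysis because the study is open-label and the rule should not be chosen during programming.

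**What to change.** 1. In SAP 3.11.3, delete the start of other therapy from the PFS event list. Keep censoring at the last assessment before new anticancer therapy, as the paragraph and Table 5 already provide.
2. In Tables 4 and 5, add to the two discontinuation rows the limit *and no later documented PD or death before new anticancer therapy*. Give both rows one censoring date: the last assessment with no documented progression. If the sponsor does intend to censor at discontinuation, state that in the PFS and DOR paragraphs of 3.11.3 instead.
3. Correct the DOR reference to section 6.2.3 and the duplicated number 6.2.1.

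Optionally, add one sentence on progression documented after a stop for undocumented clinical progression.

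The cost is SAP wording only: one deletion, a limit and a common date on two rows in each table, and a cross-reference. No new data are needed.

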3.13. Safety Analysis

3.13.1. General Considerations

All safety endpoints will be summarized for the Safety Population.

3.13.2. Adverse Events

Analyses of AEs will include only "treatment-emergent" AEs (TEAEs). TEAEs are defined as any AE that begins on or after the first administration of the study drug. Events where the onset date was the same as the study drug start date will be assumed to be treatment-emergent, unless the study drug start time and the AE start time are collected, and the AE start time is prior to the study drug start time. If an incomplete onset date is collected for an AE, the AE will be assumed to be treatment-emergent unless there is evidence that confirms that the AE was not treatmentemergent (eg, the AE end date is prior to the date of the first dose of study drug). No imputation will be performed for partial dates for AE. Analyses will not include those that have an onset greater than 30 days after study drug discontinuation.

Treatment-related AEs reported beyond 30 days after study drug discontinuation will be summarized separately during post treatment discontinuation period.

TEAEs will be summarized by Preferred Term (PT) within a System Organ Class (SOC) according to the Medical Dictionary for Regulatory Activities (MedDRA) version 21.0 or higher.

Patients reporting more than one AE within a SOC will be counted only once for that SOC. Patients reporting the same AE more than once will be counted only once for that PT. For summaries of TEAEs by the National Cancer Institute Common Terminology Criteria for Adverse Events (NCI CTCAE 5.0) grade, at each level of summation each patient is counted only once at the maximum grade level. The possible grade levels are 1 to 5, and unknown. If a patient had an AE with unknown grade, then the patient will be counted in the grade category of "unknown," even if the patient had another occurrence of the same event with a grade of 1 or 2. If the patient had another occurrence of the same AE with a grade of 3, 4 or 5, the patient will be counted under the grade 3, 4 or 5 categories based on the maximum grade level reported.

The number and percentage of patients experiencing at least one TEAE will be further summarized as follows.

- Any TEAE
- Any TEAE experienced by $\geq 10\%$ of patients
- Any TEAE with NCI CTCAE toxicity \geq Grade 3
- Any TEAE broken down by maximum NCI CTCAE toxicity grade (severity)
- Any TEAE related to ALKS 4230 as assessed by the Investigator
- Any TEAE related to pembrolizumab as assessed by the Investigator
- Any TEAE with NCI CTCAE toxicity ≥Grade 3 and related to ALKS 4230 as assessed by the Investigator
- Any TEAE with NCI CTCAE toxicity ≥Grade 3 and related to pembrolizumab as assessed by the Investigator
- Any Treatment Emergent Serious Adverse Event (SAE)
- Any SAE related to ALKS 4230 as assessed by the Investigator
- Any SAE related to pembrolizumab as assessed by the Investigator
- Any SAE related to ALKS 4230 with NCI CTCAE
 Grade 3 as assessed by the Investigator
- Any SAE related to pembrolizumab with NCI CTCAE > Grade 3 as assessed by the Investigator
- Any TEAE leading to discontinuation of ALKS 4230
- Any TEAE leading to dose interruption of ALKS 4230
- Any TEAE leading to dose reduction of ALKS 4230
- Any TEAE leading to discontinuation of pembrolizumab
- Any TEAE leading to death

The tables will be sorted by overall descending frequency of SOC and then, within a SOC, by overall descending frequency of PT based on the patient count for the overall column.

The original date and time will be shown on all listings of AEs. Listings will be provided for all TEAEs, serious TEAEs, and TEAEs leading to study treatment discontinuation. The data listings will be provided for dose reductions, and dose interruptions along with the AE/SAE that was associated with the change in dosing for ALKS 4230 and pembrolizumab separately.

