Pembrolizumab is to be administered as an IV infusion over 30 minutes in a dose of 200 mg Q3W, for up to 1 year for as long as patients are deriving clinical benefit (ie, objective response or SD) and tolerating therapy well.

Reference Therapy, Dosage, Duration, and Mode of Administration: None

**Duration of Study:** This study consists of a 28-day screening period, treatment period, and 30-day post-treatment follow-up. The treatment period consists of at least five 3-week cycles that can repeat for up to 1 year.

**Efficacy Endpoints:** The primary efficacy endpoint is the rate of new or improved antitumor response after the addition of ALKS 4230 treatment in patients receiving ongoing anti-PD-1 therapy but who have not achieved a CR.

The secondary efficacy endpoints in this study include:

- 1. Duration of response, progression-free survival, time to progression, rate of non-progression at 6 months, and OS
- 2. Antitumor response rate of subsets of patients based on disease status (PR, SD, or PD) at

screening

3. Antitumor activity as measured by radiological assessment compared to screening

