## **12.1.** Definition of Adverse Event

An AE is any untoward medical occurrence in a patient or clinical investigation patient who has been administered a pharmaceutical product. The occurrence, which may or may not have a causal relationship with the investigational treatment, may include any clinical or laboratory change that does not commonly occur in that patient and is considered clinically significant.

Illnesses present prior to the patient signing the informed consent form (ICF) are considered to be preexisting conditions and are documented on the medical history eCRF. Preexisting conditions that worsen during the study are entered on the AE eCRF.

All out-of-range laboratory values will be deemed as clinically significant or not clinically significant by the Investigator. Clinically significant values will be considered AEs and will be recorded as such on the eCRFs.

Progressive disease is not considered an AE. Death due to PD is not considered an SAE (see Section 12.5.1). Disease progression and outcome, as assessed by the Investigator, will be recorded on the eCRF.

Pregnancy is not considered an AE, although a patient will be withdrawn from the study if a pregnancy occurs. As described in Section 8.4.1, the pregnancy, including a partner's pregnancy, must be reported to Alkermes in an expedited manner similar to an SAE (Section 12.5), and additional follow-up may be required.

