# 12.3.1. Toxicity Management for Immune-related Adverse Events Associated with Pembrolizumab

AEs associated with pembrolizumab exposure may represent an immunologic etiology. These immune-related AEs (irAEs) may occur shortly after the first dose or several months after the last dose of pembrolizumab treatment and may affect more than one body system simultaneously. Therefore, early recognition and initiation of treatment is critical to reduce complications. Based on existing clinical study data, most irAEs were reversible and could be managed with interruptions of pembrolizumab, administration of corticosteroids, and/or other supportive care. For suspected irAEs, ensure adequate evaluation to confirm etiology or exclude other causes. Additional procedures or tests such as bronchoscopy, endoscopy, and skin biopsy may be included as part of the evaluation. Based on the severity of irAEs, withhold or discontinue the ALKS 4230 + pembrolizumab combination regimen and administer corticosteroids. Dose modification and toxicity management guidelines for irAEs associated with pembrolizumab are provided in Table 14.

[figure not shown]

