## 12.4. Monitoring and Recording of Adverse Events

Adverse event data collection will begin after a patient signs the ICF and will continue until completion of the Safety Follow-up Visit for the main part of the study. Long-term collection of AE data is described in Table 5. Any AE or SAE having an onset after the Safety Follow-up Visit will not be collected or reported unless the Investigator feels that the event may be related to the study drug.

The Week 3 AE review can be captured via telephone; no visit is required.

Patients will be instructed by the Investigator or designee to report the occurrence of any AE. All volunteered, elicited, and observed AEs are to be recorded on the AE eCRFs.

The Investigator will assess all AEs regarding any causal relationship to the study drug(s) (see Section 12.3), the intensity (severity) of the event, action taken, and patient outcome. For AEs not clearly related to either ALKS 4230 or pembrolizumab individually, the most conservative approach to treating the event should be used.

The following criteria should be used to guide the assessment of intensity (severity):

- Mild: Causes awareness of sign or symptom, but is easily tolerated; does not interfere with usual activities
- Moderate: Causes discomfort enough to interfere with usual activities
- Severe: Is incapacitating; results in inability to work or perform usual activities

All AEs will be followed until resolution, until deemed stable by the Investigator, or until the patient is deemed by the Investigator to be lost to follow-up.

Immune-mediated AEs will be documented as such using the immune-mediated AE eCRF.

For clinical study safety reporting purposes, the most recent version of the ALKS 4230 IB and the Keytruda USPI will be used as the reference document to designate event expectedness.

Withdrawal from the study as a result of an AE, and any therapeutic measures that are taken, shall be at the discretion of the Investigator. If a patient withdraws from the study for any reason, any ongoing AEs will be followed until resolution, until deemed stable by the Investigator, or until the patient is deemed by the Investigator to be lost to follow-up.

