# **13.5.** Safety and Tolerability Analyses

Safety will be evaluated based on the occurrence of AEs, vital signs, results of clinical laboratory tests, and ECG findings. Reported AE terms will be coded using the Medical Dictionary for Regulatory Activities (MedDRA®) version 21 preferred terms and system organ classes.

Treatment-emergent AEs (TEAEs) are defined as any AE that begins on or after the first administration of the study drug. Adverse event severity will be graded according to the CTCAE v5.0 and terms recorded on the CRFs will be mapped to preferred terms using the most recent version of the Medical Dictionary for Drug Regulatory Activities (MedDRA).

All AEs will be listed. The incidence of TEAEs will be summarized for each group and overall, by severity, and by relationship to study drug as assessed by the Investigator. The summary tables will include the number and percentage of patients with TEAEs overall, by system organ class, and by preferred terms within each system organ class. Similar tables will be prepared for SAEs, TEAEs leading to discontinuation, as well as additional categories of AEs as defined in the SAP.

Results of clinical laboratory tests will be summarized by visit for the absolute value and for change from baseline. Tables showing the shift from baseline will also be presented.

ECG findings will be listed.

Concomitant medications will be categorized and presented using the World Health Organization Anatomical Therapeutic Chemical (WHO-ATC) drug classification system.

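### TEAEs are defined by onset date alone, so an AE that starts between consent and first dose and worsens on the combination can be missing from the AE tables and TEAE listings

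*SAP*

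**What the plan says.** SAP 3.13.2 gives the rule: "TEAEs are defined as any AE that begins on or after the first administration of the study drug". The same section restricts AE analyses to TEAEs and provides AE listings for TEAEs, serious TEAEs and TEAEs leading to treatment discontinuation.

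The SAP takes the definition from Protocol 13.5: "Treatment-emergent AEs (TEAEs) are defined as any AE that begins on or after the first administration of the study drug". That protocol section also promises a listing of all AEs, which the SAP does not carry over. SAP 5 reports no change to the protocol's statistical methods, and SAP 5.1 records only a revised Efficacy Evaluable Population.

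On collection, Protocol 12.4 says "Adverse event data collection will begin after a patient signs the ICF and will continue until completion of the Safety Follow-up Visit". Events before dosing are therefore recorded. The protocol synopsis (Duration of Study) says "This study consists of a 28-day screening period, treatment period, and 30-day post-treatment follow-up". Protocol 8.3.12.1 and the Table 4 footnote on baseline tissue allow the pretreatment biopsy up to 42 days before Day 1.

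Protocol 12.1 contains the only provision on worsening: "Preexisting conditions that worsen during the study are entered on the AE eCRF". It defines preexisting conditions as illnesses already present when the consent form is signed.

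**The concern.** A TEAE definition normally has two limbs: new onset after first dose, and worsening after first dose of something that began earlier. Here the second limb is missing. Protocol 12.1 partly replaces it for illnesses present before consent, but nothing replaces it for AEs that first appear between consent and first dose.

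The gap matters more in an add-on trial of this kind. Inclusion criterion 7 and exclusion criterion 5 admit patients whose last anti-PD-(L)1 dose was 3 weeks earlier, or 2 weeks for an agent given every 2 weeks. Protocol 12.3.1 says immune-related AEs "may occur shortly after the first dose or several months after the last dose of pembrolizumab treatment". A low-grade immune-related event with first onset during screening is therefore foreseeable. If it becomes severe once ALKS 4230 is added, it bears directly on the secondary objective of safety and tolerability, and the AE tables should show it.

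**Working it through.** The plan gives no figure to reproduce, so the check sets the provisions side by side and follows an event through them.

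**1. Length of the window.** Table 4 places screening at Day -28 to Day -1, so at most 28 days. A biopsy taken 6 weeks early under study consent extends this to 6 × 7 = 42 days. Both are ceilings, not a typical patient's time at risk.

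**2. Which rule catches worsening, by time of first appearance.**
- *Before consent:* Protocol 12.1 sends the worsening to the AE form, though it gives no start-date rule.
- *Between consent and first dose:* the event is already an AE under Protocol 12.4. No provision covers its worsening.
- *On or after first dose:* it is a TEAE by definition.
- *Incomplete onset date:* SAP 3.13.2 treats the event as treatment-emergent unless there is evidence otherwise. The gap is thus confined to AEs whose onset is known to be before dosing.

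**3. Trace of a hypothetical event.** Take a Grade 1 rash with onset on Day -10 that becomes Grade 3 on Cycle 1 Day 8, is judged related and stops treatment.
- *Kept as one record dated Day -10:* it is not a TEAE. It is absent from the any-TEAE, Grade 3 or higher, related and leading-to-discontinuation summaries, and from the TEAE listings. Had it become serious, it would be absent from the serious TEAE summary as well.
- *Worsening entered as a new record dated Cycle 1 Day 8:* it is a TEAE and is counted in all of them.

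The current wording therefore gives opposite answers depending on a recording convention that neither document states. Dataset and programming specifications are deferred to separate documents (SAP 6 and 8).

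**4. Outputs that do not depend on the TEAE flag.**
- SAP 3.13.4: CTCAE grade shifts for hematology and chemistry, Grade 3 or higher laboratory listings, and the count of events of clinical interest.
- SAP 3.13.5 to 3.13.7: vital signs, ECG and the ECOG shift table.
- SAP 3.13.3: death listings.
- SAP 3.13.2: listings of dose reductions and interruptions with the associated AE or SAE.
- SAP 3.3: discontinuations from study by reason, with adverse event as one reason.

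A laboratory abnormality that worsens would appear in the shift table under either convention. The rash would not. Because it stops treatment, it would count under adverse event in the disposition table, since Protocol 9.5.2 says a patient who permanently stops study therapy should leave the study. That table does not give the event term, grade or relatedness.

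**5. Effect on a count.** SAP 3.13.2 counts each patient once at maximum grade. One lost Grade 3 event lowers the number of patients with any Grade 3 or higher TEAE by 1 if that patient has no other such TEAE, and by 0 otherwise. The count for the specific preferred term can still fall by 1 when the overall count does not.

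**The case against.** The best reply is that the loss is conditional. If sites enter a worsening as a new AE with its own date, the onset-only definition counts it correctly. That is true, but nothing in the documents tells sites to do so. An unstated convention could also differ between sites, which would make the counts depend on site practice.

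A reader might infer that such an event vanishes from every safety table. The documents do not support that. Several outputs ignore the TEAE flag, and the disposition table would count a patient who stopped because of the event. The claim reaches only the AE summary tables and the TEAE listings.

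A reader might also infer that immune toxicity carried over from earlier anti-PD-(L)1 therapy is lost in general. It is not. If it was present at consent, it is a preexisting condition and its worsening goes on the AE form. Only first onset between consent and dosing falls in the gap.

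Eligibility narrows the gap further. Exclusion criterion 18 bars gastrointestinal disorders causing diarrhea of any grade, so new diarrhea in screening would generally exclude the patient. Exclusion criterion 4 bars reversible toxicity from prior therapy that has not recovered to baseline or Grade 1 or lower. Low-grade rash and similar events remain possible.

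Finally, the 28-day and 42-day limits might be read as each patient's exposure, or each lost event as lowering the Grade 3 or higher count by 1. The limits are maxima, and the count falls only under the condition in step 5 of the working.

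**Conclusion.** The point holds in a limited form. An AE that first appears between consent and first dose, has a known pre-dose onset date and worsens on the combination is left out of the AE summary tables and TEAE listings if the worsening stays under the original onset date. The result rests on that recording assumption, which the documents neither confirm nor exclude.

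The number of affected patients cannot be derived from the documents. The direction can: an omission of this kind can only lower reported TEAE counts. The SAP's narrowing of the AE listing from all AEs to TEAEs removes the place where a reader could have found these events. The primary endpoint is not affected. This should be corrected, but it does not threaten the trial's main result.

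**What to change.** Three changes are needed.
- In SAP 3.13.2 and Protocol 13.5, define a TEAE as an AE that begins, or increases in CTCAE grade or becomes serious, on or after the first dose of either study drug.
- Instruct sites, in the eCRF completion guidance, to enter such worsening as a new AE record with its own start date. Without a date for the grade change, the revised definition cannot be programmed from a single record. With it, a program based on onset date still works.
- Restore in the SAP the listing of all AEs that Protocol 13.5 promises.

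The cost is one sentence in each document, one eCRF instruction and one listing. TEAE rates will rise slightly and some AE records will be split. Splitting does not inflate the patient counts, because SAP 3.13.2 counts each patient once per preferred term and at maximum grade.
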